8.1.13 Side Effects

Information about common side effects already known about the investigational drug can be found in the Investigators' Brochure.

- 8.1.13.1 Gastrointestinal disorders:
 - Stomatitis
 - Diarrhea
 - Abdominal pain
 - Nausea
 - Vomiting
 - Constipation
 - Dry mouth
- 8.1.13.2 General disorders and administration site conditions:
 - Fatigue/malaise
 - Edema (general and peripheral)
 - Fever
 - Asthenia
- 8.1.13.3 Infections and infestations
 - Nasopharyngitis/rhinitis/URI
 - Urinary tract infection
- 8.1.13.4 Investigations
 - Weight decreased
- 8.1.13.5 Metabolism and nutrition disorders
 - Decreased appetite
 - Diabetes mellitus
- 8.1.13.6 Musculoskeletal and connective tissue disorders
 - Arthralgia
 - Back pain
 - Pain in extremity
 - Muscle spasms
- 8.1.13.7 Nervous system disorders
 - Headache/migraine
 - Dysgeusia
 - Dizziness
- 8.1.13.8 Psychiatric disorders
 - Insomnia

8.1.13.9 Respiratory, thoracic and mediastinal disorders

- Cough/productive cough
- Epistaxis
- Dyspnea/dyspnea exertional
- Pneumonitis
- Oropharyngeal pain

8.1.13.10 Skin and subcutaneous disorders

- Rash
- Nail disorders
- Pruritus/pruritus generalized
- Dry skin/xeroderma

8.1.13.11 Vascular disorders

Hypertension

8.1.13.12 Laboratory abnormalities

- Anemia
- Thrombocytopenia
- Lymphopenia
- Neutropenia
- LFT derangement
- Renal function abnormality
- Hypercholesterolemia

8.1.14 Nursing/Patient Implications

• Non-infectious Pneumonitis

Warn patients of the possibility of developing non-infectious pneumonitis. In clinical studies, some non-infectious pneumonitis cases have been severe and occasionally fatal. Advise patients to report promptly any new or worsening respiratory symptoms.

Infections

Inform patients that they are more susceptible to infections while being treated with everolimus/placebo and that cases of hepatitis B reactivation have been associated with everolimus/placebo treatment. In clinical studies, some of these infections have been severe (e.g., leading to respiratory or hepatic failure) and occasionally fatal. Patients should be aware of the signs and symptoms of infection and should report any such signs or symptoms promptly to their physician.

Oral Ulceration

Inform patients of the possibility of developing mouth ulcers, stomatitis, and oral mucositis. In such cases, mouthwashes and/or topical treatments are recommended, but these should not contain alcohol or peroxide.

Renal Failure Events

Inform patients of the possibility of developing kidney failure. In some cases kidney failure has been severe and occasionally fatal. Inform patients of the need for the healthcare provider to monitor kidney function, especially in patients with risk factors that may impair kidney function.

Laboratory Tests and Monitoring

Inform patients of the need to monitor blood chemistry and hematology prior to the start of everolimus/placebo therapy and periodically thereafter.

• Drug-drug interactions

Advise patients to inform their healthcare providers of all concomitant medications, including over-the-counter medications and dietary supplements. Avoid concurrent treatment with strong CYP3A4 inhibitors. Use caution if everolimus/placebo must be coadministered with moderate CYP3A4 and/or PgP inhibitors; reduce the dose and carefully monitor the patient for undesirable effects. Avoid concurrent treatment with strong CYP3A4 inducers. If everolimus/placebo must be co-administered with strong CYP3A4 inducers, consider a dose increase and carefully monitor the patient for clinical response.

Patients should avoid eating grapefruit and citrus fruits or drinking their juices while in the study. The juices in these fruits can change the way the body treats or breaks down everolimus (Afinitor®).

Hepatic Impairment

Advise patients that everolimus/placebo is not recommended in patients with severe hepatic impairment (Child-Pugh class C). For advanced PNET and advanced RCC patients with moderate hepatic impairment (Child-Pugh class B), prescribe a reduced dose of 5 mg everolimus per day. For SEGA patients with moderate hepatic impairment (Child-Pugh class B), adjustment to the starting dose may not be needed. However, subsequent dosing should be individualized based on therapeutic drug monitoring.

Vaccinations

Advise patients to avoid the use of live vaccines and close contact with those who have received live vaccines.

Pregnancy

Advise female patients of childbearing potential and sexually active males that everolimus/placebo may cause fetal harm and that a highly effective method of contraception or abstinence must be used during therapy with everolimus/placebo and for 8 weeks after ending treatment.

Women of child-bearing potential, defined as all women physiologically capable of becoming pregnant, must use highly effective contraception during the study and for 8 weeks after

stopping treatment. Highly effective contraception is defined as either:

- Total abstinence: When this is in line with the preferred and usual lifestyle of the subject. [Periodic abstinence (e.g., calendar, ovulation, symptothermal, post-ovulation methods) and withdrawal are not acceptable methods of contraception]
- Sterilization: have had surgical bilateral oophorectomy (with or without hysterectomy) or tubal ligation at least six weeks before taking study treatment. In case of oophorectomy alone, only when the reproductive status of the woman has been confirmed by follow up hormone level assessment
- Male partner sterilization (with the appropriate post-vasectomy documentation of the absence of sperm in the ejaculate). [For female subjects on the study, the vasectomised male partner should be the sole partner for that subject].
- Use of a combination of any two of the following (a+b or a+c or b+c):
 - a. Use of oral, injected, implanted or other hormonal methods of contraception
 - b. Placement of an intrauterine device (IUD) or intrauterine system (IUS)
 - c. Barrier methods of contraception: Condom or Occlusive cap (diaphragm or cervical/vault caps) with spermicidal foam/gel/film/cream/vaginal suppository

In case of use of oral contraception, women should have been stable on the oral agent before taking study treatment.

Sexually active males must use a condom during intercourse while taking the drug and for 8 weeks after stopping treatment and should not father a child in this period.

A condom is required to be used also by vasectomised men in order to prevent delivery of the drug via seminal fluid.

Female partners of male patients should also be advised to use one of the following contraception methods: Use of (1) oral, injected, implanted or other hormonal methods of contraception, or (2) intrauterine device (IUD) or intrauterine system (IUS), or (3) prior male/female sterilization.

Dosing Instructions

Inform patients to take everolimus/placebo orally once daily at the same time every day, either consistently with food or consistently without food. The tablets should not be crushed or chewed. Everolimus/placebo should be swallowed whole with a glass of water. For patients unable to swallow tablets, everolimus/placebo tablet(s) should be dispersed completely in a glass of water (containing approximately 30 mL) by gently stirring, immediately prior to drinking. The glass should be rinsed with the same volume of water and the rinse should be completely swallowed to ensure that the entire dose is administered.

If vomiting occurs, no attempt should be made to replace the vomited dose.

Instruct patients that if they miss a dose of everolimus/placebo, they may still take it up to 6 hours after the time they would normally take it. If more than 6 hours have elapsed, they should be instructed to skip the dose for that day. The next day, they should take everolimus/placebo at the usual time. Warn patients to not take 2 doses to make up for the one that they missed.

8.1.15 **References**

9. Statistical Considerations

Endpoints

Primary endpoint: Disease free survival Secondary endpoints: Overall survival

The definitions of primary and secondary endpoints are described in Section 9.3.

Sample size with power justification

The trial will be a randomized double-blinded, placebo-controlled Phase II design with patients equally randomized between everolimus (Arm A) or placebo (arm B.) Randomization will be stratified on the factors outlined in Section 4. A total of 150 patients will be needed to accrue 144 randomized eligible cases. The study seeks to establish an improvement in the primary endpoint, which is defined as an 80% increase in median disease-free survival (DFS) from 15 months in the control arm (Arm B) to 27 months in the experimental arm (Arm A). The study is designed to have 90% power for a 44% reduction in the hazard rate with 144 eligible patients and 82 DFS events (as total information) which are expected to occur with 38 months of accrual at 4 patients per month and 7 additional months of follow-up, using a log-rank test at a one-sided significance level of 0.10. Under exponential distributions the hypothesized reduction corresponds to the improvement in median DFS from 15 months to 27 months and 3-year diseasefree survival of 39.7% in Arm A versus 18.9% in Arm B. The sample size was computed using seqopr6 (part of the study design library at the ECOG-ACRIN Statistical Office).

Analysis plan including plans for formal interim analysis

The primary analysis set will include all randomized eligible patients. Diseasefree survival (DFS) is defined as time from randomization to the earlier of documented recurrence (a return of tumor imaged by CT or MRI, new invasive primary cancer, or death without recurrence). Patients alive without documented recurrence or secondary primary reported will be censored at the time of the last documented disease evaluation. Tumor recurrence will be evaluated using evaluation criteria defined in Section 6 for a return of tumor imaged by CT or MRI. In the secondary analyses, overall survival (OS) is defined as time from randomization to death from any cause, censoring cases who are alive at the date of last contact. Kaplan-Meier estimates will be used for event-time distributions. DFS and OS by arm will be compared using one-sided stratified log-rank tests. Cox's proportional hazards models will be used to estimate hazard ratios. Toxicity will be assessed through summaries of adverse events by arm. Formal comparison of toxicity rates between the arms is not a goal of this trial and the sample size will provide sufficient power for detecting only relative large difference in adverse events. With 75 patients per arm, the study will have sufficient precision to provide 90% confidence interval on toxicity that will be no wider than 20%. For rare toxicities with 2% true probability, there will be 78% probability of observing one or more toxicities in either treatment arm. For rare toxicities with 3% true probability, there will be 90% probability of observing one or more toxicities on either treatment arm. Patient demographics and disease characteristics will be compared using two-sample t-tests or Fisher's exact tests

with a two-sided significance level of 0.10 as appropriate. Stratification will be used to ensure balance between groups and not for subset analysis.

The study will be monitored for potential efficacy stopping using an early look at DFS after approximately 50% of the planned full information (41/82 DFS events) has been observed. A one-sided log-rank test for DFS will be performed for the monitoring analysis. To preserve the overall type I error rate at 0.10, a critical value at the interim analysis will be determined using the O'Brien-Fleming boundary. Under the planned accrual schedule with four patients per month (3.8 eligible patients/ month), the monitoring analysis is projected to occur at 28.3 months following the start of accrual. If the true control median DFS is 15 months and the true experimental median DFS is 27 months, there will be 42% probability of crossing the upper efficacy boundary (2.05).

This study will also be monitored for futility using a rule that the study will be stopped early for lack of benefit if the estimated hazard ratio for experimental/control ≥ 1 at 50% of the planned full information. There will be 50% probability of early termination under the null hazard ratio of 1.0 (experimental/control) and 3.6% probability of early termination under the target alternative hazard ratio of 0.56 (experimental/control).

Safety Monitoring

Interim analyses of toxicity are performed twice yearly for all ECOG-ACRIN studies. Reports of these analyses are sent to the ECOG-ACRIN Principal Investigator or Senior Investigator at the participating institutions. Expedited reporting of certain adverse events is required, as described in Section 5.2.

Study Monitoring

This study will be monitored by the ECOG-ACRIN Data Safety Monitoring Committee (DSMC). The DSMC meets twice each year. For each meeting, all monitored studies are reviewed for safety and progress toward completion. When appropriate, the DSMC will also review interim analyses of outcome data. Copies of the toxicity reports prepared for the DSMC meetings are included in the study reports prepared for the ECOG-ACRIN group meeting (except that for double blind studies, the DSMC may review unblinded toxicity data, while only pooled or blinded data will be made public). These group meeting reports are made available to the local investigators, who may provide them to their IRBs. Only the study statistician and the DSMC members will have access to interim analyses of outcome data. Prior to completion of this study, any use of outcome data will require approval of the DSMC. Any DSMC recommendations for changes to this study will be circulated to the local investigators in the form of addenda to this protocol document. A complete copy of the ECOG-ACRIN DSMC Policy can be obtained from the ECOG-ACRIN Operations Office - Boston.

Gender and Ethnicity

Based on data from E6201 the anticipated accrual in subgroups defined by gender and race is:

Ethnic Category	Gender			
	Females	Males	Total	
Hispanic or Latino	3	3	6	
Not Hispanic or Latino	66	78	144	
Ethnic Category: Total of all subjects	69	81	150	

Racial Category			
American Indian or Alaskan Native	0	0	0
Asian	1	1	2
Black or African American	5	5	10
Native Hawaiian or other Pacific Islander	0	0	0
White	63	75	138
Racial Category: Total of all subjects	69	81	150

The accrual targets in individual cells are not large enough for definitive subgroup analyses. Therefore, overall accrual to the study will not be extended to meet individual subgroup accrual targets.

10. Specimen Submissions

Fixed paraffin-embedded metastatic tumor from core biopsy or surgery must be submitted for central diagnostic review and classification. Primary tumor tissue, if available, is also requested. Blood specimens and frozen tissue, if available, are to be submitted for use in research from consenting patients. Descriptions of the diagnostic review and examples of potential research studies are in Section 11.

SAMPLE TRACKING SYSTEM (STS): All specimens submitted on this trial must be entered and tracked using the ECOG-ACRIN Sample Tracking System. Any case reimbursements associated with specimen submissions to ECOG-ACRIN–designated laboratories will be determined only from data contained in STS.

LABELING: Specimens are to be labeled clearly with the ECOG-ACRIN protocol number "E2212", patient initials, date and time of collection, and sample type. All sample submissions are to be accompanied with an STS shipping manifest.

SHIPPING ACCOUNT: Samples shipped to the ECOG-ACRIN PCORL or [name] Laboratory are to be shipped using the PCORL's FedEx account using the FedEx On-Line Services. Access to the shipping account for specimen shipments to the ECOG-ACRIN PCORL at Northwestern University can now only be obtained by logging into fedex.com with an account issued by the ECOG-ACRIN PCORL. For security reasons, the account number will no longer be given out in protocols, over the phone, or via email. If your site needs to have an account created, please contact the ECOG-ACRIN PCO by email at [contact]

Submissions to the (PCORL) - MANDATORY

The ECOG-ACRIN Pathology Coordinating Office-Reference Laboratory (PCORL) is the receiving laboratory for all specimens submitted from patients participating in this trial.

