The OPEN system will provide the site with a printable confirmation of NOTE: registration and treatment information. Please print this confirmation for your records.

Further instructional information is provided on the OPEN tab of the CTSU members' side of the CTSU website at https://www.ctsu.org or at https://open.ctsu.org. For any additional guestions contact the CTSU Help Desk at [name] or [contact]

Randomization

Please note that no blinded starter supplies will be available for this study. At the time of patient randomization each patient will be assigned a specific blinded drug ID number (e.g. DR117). This blinded drug ID number should be included on the drug request form that is submitted to the ECOG-ACRIN Drug Team. (See Section 8 for complete details.)

Please note that when a patient has been successfully randomized, the confirmation of randomization will indicate that the patient is on arm X. The patient will actually be randomized to arm A or B, but as this is a doubleblind trial, that information cannot be displayed.

At time of randomization, the following information will be requested:

- 4.1.1 Protocol Number
- 412 Investigator Identification
 - Institution and affiliate name
 - Investigator's name
- 4.1.3 Patient Identification
 - Patient's initials (first and last)
 - Patient's Hospital ID and/or Social Security number
 - Patient demographics
 - Gender •
 - Birth date (mm/yyyy)
 - Race
 - Ethnicity
 - Nine-digit ZIP code
 - Method of payment
 - Country of residence

Eligibility Verification

Patients must meet all of the eligibility requirements listed in Section 3.

Stratification Factors

Stratification will only be used to ensure balance between groups, not for subset analysis. There are three stratification factors as follows:

- 4.3.1 R0 versus R1 resection
- 4.3.2 Primary tumor resection

- 4.3.2.1 Primary tumor resection with metastasectomy
- 4.3.2.2 Primary tumor resection prior to metastasectomy
- 4.3.3 Resection ± ablation
 - 4.3.3.1 RF or microwave ablation plus resection
 - 4.3.3.2 Resection alone

Additional Requirements

4.4.1 Patients must provide a signed and dated, written informed consent form.

NOTE: Copies of the consent are not collected by the ECOG-ACRIN Operations Office – Boston.

- 4.4.2 Pathological samples are **required** to be submitted for central diagnostic review as indicated in Section 10.
- 4.4.3 Biological samples to be submitted for research as outlined in Section 10.

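### Does the interim stopping rule need rewording because it does not say whether its log-rank test and hazard ratio are stratified?

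*Combined protocol and SAP*

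**What the plan says.** All the relevant text is in Section 9, apart from the list of factors in Section 4.3.

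- Sample size with power justification: randomization is stratified on the Section 4 factors, and the trial is sized "using a log-rank test at a one-sided significance level of 0.10". The word stratified is missing here too, although this is the main comparison.
- Analysis plan including plans for formal interim analysis: "DFS and OS by arm will be compared using one-sided stratified log-rank tests". Hazard ratios come from Cox models ("Cox's proportional hazards models will be used to estimate hazard ratios"), with no mention of strata or covariates.
- Same subsection, interim efficacy: "A one-sided log-rank test for DFS will be performed for the monitoring analysis". The O'Brien-Fleming bound is 2.05, with a stated 42% chance of crossing it at the target effect.
- Same subsection, futility: stop for "the estimated hazard ratio for experimental/control ≥ 1 at 50% of the planned full information". The stated stopping probabilities are 50% under the null and 3.6% at the target.
- Section 4.3: three two-level factors (resection margin, timing of primary resection, ablation or not). It adds "Stratification will only be used to ensure balance between groups, not for subset analysis".
- Study Monitoring: "Only the study statistician and the DSMC members will have access to interim analyses of outcome data".

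**The concern.** A stopping rule should give one answer for one data set. Here the efficacy test could be stratified or plain, and the futility hazard ratio could come from a stratified or plain Cox model, so there are at least two readings, and more if they are mixed. The statement in Section 4.3 that stratification serves balance does not settle it, because that sentence rules out subset analyses and says nothing about the test.

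With 41 events spread over up to 8 cells, the two versions will sometimes fall on opposite sides of a boundary. Those who would then have to choose are the study statistician and the DSMC, who see the unblinded results. If the choice could be made after seeing both answers, a trial might stop or continue on a decision not fixed in advance.

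**Working it through.** **1. Reproduce the plan's figures (plain log-rank, equal hazards across strata).** Inputs from Section 9: medians 15 and 27 months, so HR = 15/27 = 0.556; 1:1 allocation; looks at 41 and 82 events; one-sided alpha 0.10.

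- Lan-DeMets O'Brien-Fleming spending at half information: alpha spent = 2[1 − Φ(1.645/√0.5)] = 0.020, so the bound is 2.054 (stated 2.05).
- Mean of the interim Z = −ln(HR) × √41/2 = 0.588 × 3.202 = 1.882.
- Interim crossing = 1 − Φ(2.05 − 1.882) = 43.3%. With HR 0.56 the mean is 1.856 and the crossing 42.3% (stated 42%).
- Futility stop at the target = Φ(−1.882) = 3.0%, or 3.2% with HR 0.56 (stated 3.6%). Under the null it is 50%.
- Power with 82 events is 91.6% for a fixed design, and 90.2% with both interim rules (stated 90%).

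**2. Link between the test and the hazard ratio.** The Cox estimate is at or above 1 exactly when the log-rank score is at or below zero, provided both use the same strata. Fixing the strata of the test therefore settles the futility rule too.

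**3. Compare the readings by simulation.** From the documents: 144 patients at 3.8 per month, exponential DFS, control median 15 months, looks at 41 and 82 events. Assumed, because the documents do not give them: permuted blocks of 4 within 8 strata, factor prevalences, and factor hazard ratios. The first set used 12,000 trials in each of nine settings under each hypothesis, with prevalences 40/50/30, 50/50/50 and 20/70/15% and factor hazard ratios 1/1/1, 1.5/1.25/1.5 and 2/1.5/2.

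| Quantity | Plain interim, stratified final | Stratified at both |
|---|---|---|
| Type I error, futility stop included | 0.090–0.099 | 0.090–0.099 |
| Power | 0.876–0.889 | 0.873–0.886 |
| Interim crossing at HR 5/9 | 41.3–42.7% (non-prognostic factors); 34.9–36.8% (strong factors) | 37.9–40.0% |
| False futility stop at HR 5/9 | 2.9–3.4% | 3.4–3.9% |

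The final conclusion differs between readings in 0.7–1.4% of trials. The interim action differs in 9.9–13.3% at HR 5/9 and 9.8–13.4% at HR 1.

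A second, separate simulation over 33 scenarios gave 9.2–12.9%, with the two interim Z values correlated at about 0.94 to 0.97. Wider assumptions moved the figure to about 7% with very unbalanced factors, 14–16% with strong factors (hazard ratios 3, 2, 2), and 3–4% when only one factor varies.

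**4. Why stratifying moves the 42%.** Stratifying over sparse cells loses a little information. At HR 0.556 with prevalences 30/40/30% and non-prognostic factors, the log-rank variance averages 10.04 plain and 9.37 stratified. The mean Z becomes about 1.882 × √(9.37/10.04) = 1.818, and the crossing 1 − Φ(2.05 − 1.818) = 41%. The simulation gave 42.6% plain and 40.3% stratified.

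**5. Put the 10–13% in proportion.** Keep the test fixed and move only the timing. The Z values at 41 and 45 events correlate at √(41/45) = 0.955, much as the stratified and plain Z values do. By normal approximation, looking at 44 or 45 events instead of 41 changes the action in about 9.4–11.1% of trials under the null and about 10–13% at HR 5/9, with the bound held or re-spent. At about 2.4 events per month under the design assumptions, 3 or 4 events take 1.2 to 1.7 months. The plan itself sets the look at approximately 50% information, and the DSMC meets twice a year.

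**The case for a change.** The best case for a change is that a rule that can end the trial should be unique before unblinding, that Section 9 does not make it so in words, and that a few words would. The stated figures do not show which test was meant: the 42% lies closer to the plain calculation, while the 3.6% falls inside the stratified range (3.4–3.9%) and just outside the plain one (2.9–3.4%). Sparse cells at 41 events could also give someone a reason to reconsider the test at the look.

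The textual point stands: the word is absent, and the Cox strata are not stated. The consequence does not carry it further. Even if someone computed both versions and always took the more favourable, null crossing at the interim would rise only from about 2% to 2.3–2.7%. Nothing in the text grants that discretion, since the general sentence on DFS comparisons already points to the stratified test. A cell with patients on one arm only contributes nothing to a stratified log-rank test, so sparse cells cost some information but do not invalidate it. Re-running the 42% would need stratum sizes and effects that the documents do not give, for a shift of about 1 to 3 points.

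**Conclusion.** No change to the plan is called for. The sentence requiring stratified log-rank tests for DFS stands under a heading that expressly includes the formal interim analysis, and the interim look is a comparison of DFS by arm. The sample-size paragraph also drops the word for the main comparison, so the omission reads as shorthand. A statistician following the plan would stratify the interim test on the three Section 4.3 factors and take the futility hazard ratio from a Cox model with the same strata.

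If someone instead ran a plain interim test, error control would still hold: type I error is 0.090–0.099 on either reading, power is within about 0.3 points, and the final conclusion differs in 0.7–1.4% of trials. The 3–16% of trials in which the interim action would differ depends on assumed prevalences, prognostic effects and block size. It reflects ordinary disagreement between two valid, highly correlated statistics. Writing the choice down would do no harm, but it would improve neither error control nor power.
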